2. INTRODUCTION

Participants will be enrolled from both active and placebo arms of qualifying efgartigimod studies in adult patients with pSS. The protocol will be amended to add additional studies at a later date.

In qualifying study ARGX-113-2106, the efficacy and safety of efgartigimod in adult patients with pSS was evaluated using a randomized, double-blinded, placebo-controlled study design. Participants were randomized to receive efgartigimod IV 10 mg/kg or matching placebo in a 2:1 ratio. The IMP (efgartigimod or matching placebo) was administered during the treatment period in approximately 1-hour IV infusion QW by site or a home nurse. The final dose was administered at week 23. At week 24, eligible participants from ARGX-113-2106 may roll over into the present single-arm OLE study: ARGX-113-2211.

2.1. Study Rationale

Efgartigimod is a first-in-class antibody fragment that binds to FcRn. This binding prevents FcRn from recycling IgG and leads to a reduction in circulating disease-causing autoantibodies. Efgartigimod is being clinically developed in autoimmune diseases mediated by pathogenic IgG autoantibodies after approval by the United States FDA, EMA, and Japan's PMDA for use in adult patients with AChR-Ab seropositive gMG.

Efgartigimod may be a viable treatment option for individuals diagnosed with pSS because it has been shown to reduce IgG levels, including IgG autoantibodies, that may underlie some of the autoimmune disease manifestations in these participants. Therefore, the reduction of autoantibodies may successfully reduce disease activity and symptoms in pSS participants.

This open-label extension study will evaluate the long-term safety of efgartigimod in participants with pSS who have completed the treatment period of the qualifying studies.

2.2. Background

Efgartigimod is a neonatal FcRn antagonist designed to treat autoimmune diseases mediated by IgG autoantibodies. pSS is a chronic, progressive autoimmune disease of unknown etiology, typically characterized by an autoimmune exocrinopathy. Along with symptoms of excessive dryness, manifestations include profound fatigue, chronic pain, extraglandular organ system involvement, and increased risk of lymphomas. A hallmark of pSS is B-cell hyperactivity, causing a vicious cycle of immune activation through cytokine production, antigen presentation, and autoantibody secretion, potentially causing tissue damage. Currently, no immunomodulatory treatment is available for pSS.

Efgartigimod, an FcRn antagonist that can rapidly reduce IgG, including pathogenic antibodies, contributes to successfully treat pSS and has the potential to improve disease manifestations by the reduction of IgG autoantibodies in pSS. This study aims to evaluate the long-term safety of efgartigimod in participants with pSS who have completed the treatment period of the qualifying studies.

A detailed description of the chemistry, pharmacology, efficacy, and safety of efgartigimod is provided in the current IB.

2.3. Benefit/Risk Assessment

More detailed information about the known and expected benefits and risks and reasonably expected AEs of efgartigimod is provided in the current IB.

2.3.1. Risk Assessment

Overall, available data confirm that efgartigimod has been well-tolerated across studies in different indications and has an acceptable safety profile.

Potential clinically significant risk	Summary of data/rationale for risk	Mitigation strategy
Serious infection	Efgartigimod reduces IgG levels, potentially hindering immune response and increasing the risk of infection.	Exclude participants with clinically significant active infection not sufficiently resolved in the investigator's opinion (Section 5.2). Infections are considered adverse event of special interest (AESI; Section 8.4.6). Monitor for infections and temporarily interrupt IMP dosing as specified in Section 7.1.
Infusion/injection-related reactions	All therapeutic proteins can elicit immune responses, potentially resulting in hypersensitivity, or allergic reactions such as rash, urticaria, angioedema, serum sickness, and anaphylactoid, or anaphylactic reactions.	Monitor participants during administration and for 30 minutes thereafter for clinical signs and symptoms of infusion/injection-related reactions. Infusion/injection-related reactions are considered AEs of clinical interest (Section 8.4.7). If an infusion reaction occurs, interrupt the infusion and implement appropriate supportive measures. Once resolved, the infusion can be resumed, and at a slower rate if necessary.
Infusion/injection site reactions	Most AEs have been mild, transient injection site reactions, including erythema, pain, bruising, pruritus, burning, tenderness, edema, induration, irritation, paresthesia, numbness, and rash. Moderate injection site reactions occurring less frequently include burning, erythema, pain, and numbness. Mild to moderate headache is commonly reported.	Continuously monitor participants for injection site reactions. Infusion/injection site reactions are considered AEs of clinical interest (Section 8.4.7).

Potential clinically significant risk	Summary of data/rationale for risk	Mitigation strategy
---------------------------------------	------------------------------------	---------------------

AE = adverse event; AESI = adverse event of special interest; IgG = immunoglobulin G; IMP = investigational medicinal product

2.3.2. Benefit Assessment

Efgartigimod has been investigated in nonclinical studies, phase 1 clinical pharmacology studies in healthy participants, and phase 2/3 clinical studies in participants with IgG-driven autoimmune diseases, including gMG, primary ITP, CIDP, and pemphigus.

In clinical studies, efgartigimod effectively reduces IgG antibody levels, including pathogenic autoantibodies. The efficacy of efgartigimod to improve clinical outcomes in gMG and reduce pathogenic autoantibodies was confirmed in a pivotal phase 3 study in participants with gMG (ARGX-113-1704). In addition, clinical benefit was observed in phase 2 studies in primary ITP (ARGX-113-1603) and pemphigus (ARGX-113-1701), in which pathogenic autoantibodies underlie the disease pathology (refer to current efgartigimod IB). Available clinical data support the clinical benefit of efgartigimod for reducing pathogenic IgG autoantibodies, which may mitigate autoimmune dysfunction and improve symptoms, as well as the ability to function, in participants with pSS.

2.3.3. Overall Benefit-Risk Conclusion

The potential risks associated with efgartigimod are justified by the anticipated benefits possibly afforded to participants with pSS in this study and considering the measures implemented to minimize risks. The favorable balance between risks and anticipated efficacy/benefit supports the use of efgartigimod in the clinical development for pSS.

More detailed information about the known and expected benefits and risks of efgartigimod and reasonably expected AEs can be found in the current IB.

3. OBJECTIVES, ENDPOINTS, AND ESTIMANDS

Table 2: Study ARGX-113-2211 Objectives and Endpoints

Objectives	Endpoints
Primary	

 To evaluate the long-term safety of efgartigimod in patients with pSS 	
 Incidence and severity of AEs and AESIs, incidence SAEs, changes in laboratory test results, vital signs, and ECG results
Secondary	

 To evaluate effect and assess long-term data on durability of CRESS response 	
 Proportion of CRESS responders on ≥ 3 of 5 items at weeks 24 and 48 (refer to Section 8.2.1). The 5 items are: 
 Systemic disease activity: clinESSDAI Patient-reported symptoms: ESSPRI Tear gland function: Schirmer’s test and OSS Salivary gland function: UWSF rate and SGUS Serology: serum IgG and/or RF

 To evaluate the effect of efgartigimod on clinical efficacy parameters 	
 Proportion of participants with minimal clinically important improvement from baseline in ESSDAI: improvement of ≥ 3 points in ESSDAI score at weeks 24 and 48 Proportion of participants with low disease activity: ESSDAI score of < 5 at weeks 24 and 48 Proportion of participants with minimal clinically important improvement from baseline in clinESSDAI: improvement of ≥ 3 points in clinESSDAI score at weeks 24 and 48 Proportion of participants with low disease activity: clinESSDAI score of < 5 at weeks 24 and 48 Proportion of participants with minimal clinically important improvement from baseline in ESSPRI: decrease of ≥ 1 point or $\geq 15\%$ at weeks 24 and 48 Change from baseline in ESSDAI score at weeks 24 and 48 Change from baseline in clinESSDAI score at weeks 24 and 48 Change from baseline in ESSPRI score at weeks 24 and 48

 To evaluate the effect of efgartigimod on STAR 	
 Proportion of STAR responders (score of ≥ 5) at weeks 24 and 48 when compared to baseline

Objectives	Endpoints

 To assess the PD effect of efgartigimod 	
 Values, changes from baseline, and percent reduction from baseline in total IgG levels in serum over the 48-week treatment period Values, changes from baseline, and percent reduction from baseline in autoantibodies in serum over the 48-week treatment period: 
 Anti-Ro/SS A Anti-La/SS B

 To assess the exposure to efgartigimod 	
 Efgartigimod serum concentrations over the 48-week treatment period

 To assess the immunogenicity of efgartigimod 	
 Incidence and prevalence of ADA against efgartigimod over the 48-week treatment period
Exploratory	

 To explore the effect of efgartigimod on additional clinical pSS measures 	
 Proportion of responders on 2 of 4 items of the adjusted CRESS (without serology item) at weeks 24 and 48 when compared to baseline Change from baseline in activity of individual ESSDAI domains at weeks 24 and 48

 To explore the effect of efgartigimod on glandular measures 	
 Change from baseline in: 
 SWSF rate at weeks 24 and 48 UWSF rate at weeks 24 and 48 Hocevar score at weeks 24 and 48 Schirmer's test at weeks 24 and 48 OSS at weeks 24 and 48 Response in salivary gland as defined in CRESS at weeks 24 and 48 when compared to baseline Response in tear gland as defined in CRESS at weeks 24 and 48 when compared to baseline

 To explore the effect of efgartigimod on patient-reported outcomes 	
 Change from baseline in: 
 Total MFI score at weeks 24 and 48 Physical component and mental component scores of SF-36 at weeks 24 and 48 PGA at weeks 24 and 48 Individual ESSPRI scores at weeks 24 and 48 EQ-5D-5L utilities and VAS scores at weeks 24 and 48 PASS at weeks 24 and 48 when compared to baseline

Objectives	Endpoints

 • CCI [REDACTED] 	
 • CCI [REDACTED] • Values, changes from baseline, and percent reduction from baseline in RF in serum over the 48-week treatment period

ADA = antidrug antibody; AESI = adverse event of special interest; clinESSDAI = clinical EULAR Sjögren’s syndrome disease activity index; CRESS = Composite of Relevant Endpoints for Sjögren’s Syndrome; ECG = electrocardiogram; ESSDAI = EULAR Sjögren’s syndrome disease activity index; ESSPRI = EULAR Sjögren’s Syndrome Patient-Reported Index; IFN = interferon; CCI [REDACTED]; IgG = immunoglobulin G; CCI [REDACTED] RF = rheumatoid factor; IV = intravenous; MFI = Multidimensional Fatigue Inventory; OSS = ocular staining score; PASS = patient acceptable symptom state; PD = pharmacodynamic(s); PK = pharmacokinetic(s); pSS = primary Sjögren’s syndrome; PT = preferred term; SAE = serious adverse event; SGUS = salivary gland ultrasonography; SOC = system organ class; STAR = Sjögren’s Tool for Assessing Response; SWSF = stimulated whole salivary flow; TEAE = treatment-emergent adverse event; UWSF = unstimulated whole salivary flow; VAS = visual analog scale.

No estimands have been defined for this study.

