4.3. Justification for Dose

Doses of efgartigimod 10 mg/kg either QW or Q2W will be administered. For responders a Q2W regimen has been selected to evaluate whether a less frequent dosing regimen can maintain clinical efficacy, while the QW regimen for nonresponders targets efgartigimod's to achieve a near maximal total IgG reduction (PD effect), thereby maximizing the chance of a clinical response on the efficacy outcomes in nonresponders.

As the hypothesis for treating pSS with efgartigimod is to reduce the pathogenic autoreactive IgG, the selected doses and dose regimen target a nearly maximal PD effect (ie, reduction of pathogenic IgGs). The chronic nature of pSS reflects the need for chronic treatment to maintain pathogenic IgG autoantibody suppression and symptom reduction.

The cumulative data from a phase 1 study in healthy adult subjects; phase 2 studies in participants with gMG, ITP, and pemphigus; phase 3 studies in gMG; and PK/PD modeling results demonstrate that a 10 mg/kg efgartigimod dose administered QW through IV infusion achieved 60% to 70% total IgG reduction, including the reduction of pathogenic autoantibodies. Maximal IgG reduction was associated with clinical efficacy observed in gMG, ITP, and pemphigus studies. Furthermore, this dose has been safe and well-tolerated in all study populations and has demonstrated similar PK and PD profiles across indications. Accordingly, the 10 mg/kg IV dose regimen (QW or Q2W) was selected for this study.

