6.2. Baseline

Unless otherwise specified, baseline is defined as the last available non-missing measurement from the parent study 2106. Refer to [appendix 1](#) baseline for details. These baseline observations could be either from week 24 or prior visits of ARGX-113-2106. All baseline assessments will be performed before first administration of efgartigimod in ARGX-113-2211, if applicable. The baseline of ECG parameters should come from the same date. If an individual

confidential and proprietary to IQVIA Holdings Inc. and its subsidiaries. Unauthorized use, disclosure or reproduction is strictly prohibited.

ECG parameter is not reported on the latest date prior to 1st IMP infusion within the extension study, leave blank. Assessments do not need to be repeated if they are performed as part of the last visit of the qualifying study. Assessments performed on the same day as the first IMP administration but without time information collected or with time information exactly equal to the time of first IMP administration and which are planned predose will be considered as predose. For parameters related to questionnaires, the baseline is the last value before or at the day of first administration of the IMP, independent of the time of administration. In case the participant never received IMP, the date/time of enrolled will be used instead of first IMP administration date/time. Adverse Events (AEs) and medications commencing on the reference start date will be considered post-baseline unless otherwise indicated based on available start date/time combination or collected electronic case report form (eCRF) information that identifies the individual event/medication as starting prior to first IMP administration.

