6.7. Values below or Above the Quantification Limit

ADA against efgartigimod: titer of positive ADA samples reported as “negative titer” (refer to [Section 16](#)) will be imputed by 1. Listings will always present “negative titer”.

Safety and PD values expressed as below (or above) the quantification limit will be imputed by the value of the quantification limit itself. For participants with a baseline PD value below/above the quantification limit, the PD parameter will be excluded from the statistical analyses involving change and percent change from baseline. Listings will always show the non-imputed values.

Pharmacokinetic concentrations below the lower quantification limit will be reported in the listings as BLQ. For descriptive statistical analysis, all BLQ values will be set to zero. Listings will always present BLQ.

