9. DEMOGRAPHIC AND OTHER BASELINE CHARACTERISTICS

Demographic and other baseline characteristics will be summarized using descriptive statistics for the FAS.

The baseline visits for study ARGX-113-2211 will be conducted after the participant has completed the qualifying study (i.e., week 24 visit ARGX-113-2106). The following demographic and other baseline characteristics will be reported for this study:

- Age (years) - calculated relative to date of consent.
- Age Category (18 - <65 years, 65 - <75 years and \geq 75 years).
- Sex
- Childbearing potential for female subjects only (Yes, No)
 - If No, then reason (Post-Menopausal, Premenarchal, Surgically Sterile, Other)
- Weight (kg)
- Height (cm) [obtained from Argenx – 113-2106]
- BMI (kg/m^2)

Copyright © 2009, 2010, 2012, 2016, 2018, 2019, 2021, 2024 IQVIA. All rights reserved. The contents of this document are confidential and proprietary to IQVIA Holdings Inc. and its subsidiaries. Unauthorized use, disclosure or reproduction is strictly prohibited.

- Anti-Ro/SS-A positive
- Anti-La/SS-B positive
- UWSF- Salivary Flow Rate
- SWSF – Salivary flow Rate
- SGUS
- OSS- Right Eye and Left Eye
- Schirmer- Right Eye and Left Eye
- Schirmer <5mm/5min in at least one eye
- RF
- ESSDAI Total score
- ESSDAI ≥ 10
- clinESSDAI score
 - Is patient a responder (Yes, No)
 - Dosing Regimen (QW, Q2W)
- ESSPRI score
- MFI Score
- SF-36 Score [Physical Component Score (PCS) and Mental Component Score (MCS)]
- Baseline IgG
- 
- 

Summary statistics including n, mean, median, SD, minimum and maximum will be presented for all continuous variables listed above. The number and percentage of subjects will be presented for categorical variables such as sex.

All demographic data and baseline characteristics will be listed as well.

[figure not shown]

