14. PHARMACODYNAMIC ANALYSIS

PD analyses will be performed in the SAF. PD endpoints include total IgG, Anti-Ro/SS-A, and anti-La/SS-B. PD endpoints will be summarized using descriptive statistics at each analysis visit. Actual values, changes from baseline, and percent change from baseline will be presented. In addition to the planned time points at baseline, week 4, 8, 12, 16, 24, 36, 48, and SFV, the following time points will also be shown:

- Maximum drop from baseline
- Minimum postbaseline value

Additionally, a line chart showing percent change in total IgG, Anti-Ro/SS-A, and anti-La/SS-B, over time will be prepared. If appropriate, the graphic presentation of percent change over time may be presented for all PD endpoints combined. All PD data will be listed.

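### For participants who come from the parent efgartigimod arm, percent change in IgG and autoantibodies is taken from an on-drug baseline and shows maintenance, not the PD effect

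*Protocol*

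**What the plan says.** Protocol section 3 (Table 2) sets a secondary objective of assessing the PD effect of efgartigimod. The endpoint for IgG is "Values, changes from baseline, and percent reduction from baseline in total IgG levels in serum over the 48-week treatment period", and anti-Ro/SS-A and anti-La/SS-B have the same form.

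On the reference value, SAP 6.2 says that "baseline is defined as the last available non-missing measurement from the parent study 2106". It allows this to come from week 24 of ARGX-113-2106 or from an earlier visit. Protocol 9.3.1 is in line with this: baseline is the last assessment before the first dose in the open-label extension (OLE).

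On the outputs, SAP 14 states: "Actual values, changes from baseline, and percent change from baseline will be presented". It adds the maximum drop from baseline and the minimum post-baseline value. SAP 7.2 gives summaries overall and by parent-study treatment.

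On what participants received before entry, protocol section 2 says: "Participants were randomized to receive efgartigimod IV 10 mg/kg or matching placebo in a 2:1 ratio". Dosing was weekly. On timing it says: "The final dose was administered at week 23. At week 24, eligible participants from ARGX-113-2106 may roll over". Inclusion criterion 4 requires treatment to continue with no break.

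On the expected size of the effect, protocol 4.3 reports that a "10 mg/kg efgartigimod dose administered QW through IV infusion achieved 60% to 70% total IgG reduction". This comes from other indications, healthy adults and modelling.

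**The concern.** Percent reduction from baseline measures a drug effect only if the baseline is free of the drug. For a participant who has just finished about 24 weeks of weekly efgartigimod, it is not. The calculation then shows how far IgG moves around an already lowered level. The same applies to the maximum drop from baseline, which for these participants can record only a further fall below that level.

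Splitting by parent arm isolates the problem but does not solve it. The former-placebo column, about 10 people, shows a reduction from an untreated level. The former-efgartigimod and overall columns do not, yet they carry the same endpoint name. A reader who compares either of them with the 60% to 70% that supports the regimen would conclude that IgG lowering is weak or absent. The table of mean IgG percent change by antidrug-antibody class (SAP 15) also uses this percent change.

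**Working it through.** The documents state no expected PD result for the OLE, so there is no planned figure to reproduce. The check asks what the planned formula would return if protocol 4.3 holds.

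**Inputs**
- Allocation 2:1 (protocol 2). The former-efgartigimod share is 2/(2+1) = 66.7%, or 20 of 30, if rollover is equal by arm (assumption). If each participant independently has this probability, the 5th to 95th percentile is 16 to 24 of 30.
- Up to approximately 30 participants (protocol 9.5).
- Last parent dose at week 23 and rollover at week 24, so baseline falls about one week after a dose.
- Reduction on weekly dosing (QW): 60% to 70% (protocol 4.3).
- Reduction on two-weekly dosing (Q2W): not given. The range 40% to 60% is an assumption, for illustration only.

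**Formulas**

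Let r be the fractional IgG reduction from the untreated level at OLE entry, and s the reduction during the OLE. Participants are treated as homogeneous.
- Former efgartigimod: percent change = 100 × [(1 − s)/(1 − r) − 1]
- Former placebo: percent change = −100 × s
- Pooled = (2/3) × former efgartigimod + (1/3) × former placebo

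**Everyone on QW, suppression unchanged (s = r)**

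| r = s | Former efgartigimod | Former placebo | Pooled |
|---|---|---|---|
| 60% | 0% | −60% | (20×0 − 10×60)/30 = −20.0% |
| 65% | 0% | −65% | (20×0 − 10×65)/30 = −21.7% |
| 70% | 0% | −70% | (20×0 − 10×70)/30 = −23.3% |

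From a pre-dose baseline, all three columns would read −60% to −70%. If suppression drifts within 60% to 70%, the former-efgartigimod column runs from 0.30/0.40 − 1 = −25% to 0.40/0.30 − 1 = +33%.

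**Former efgartigimod moved to Q2W, r = 65% (assumed s)**
- s = 60%: 0.40/0.35 − 1 = +14%
- s = 50%: 0.50/0.35 − 1 = +43%
- s = 40%: 0.60/0.35 − 1 = +71%

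**Mixed case, r = 65%: half of former efgartigimod and a quarter of former placebo on Q2W, the rest on QW at 65%**

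| Assumed Q2W reduction | Former efgartigimod | Former placebo | Pooled |
|---|---|---|---|
| 60% | +7.1% | −63.8% | −16.5% |
| 50% | +21.4% | −61.3% | −6.1% |
| 40% | +35.7% | −58.8% | +4.2% |

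**When the pooled column reaches zero**

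With a common s, set 2[(1 − s)/(1 − r) − 1] = s. This gives s = 2r/(3 − r): 50% for r = 60%, 55% for r = 65% and 61% for r = 70%. So the pooled column is diluted if suppression is maintained. It vanishes or reverses only if suppression in the OLE falls clearly below the entry level.

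No such figures can be worked out for anti-Ro/SS-A or anti-La/SS-B. Protocol 4.3 says that pathogenic autoantibodies fall too, but gives no separate size.

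**The case against.** The best defence is that baseline at OLE entry is declared in both documents and answers a sensible question. Q2W was chosen to see whether less frequent dosing maintains efficacy, and an IgG rise from entry on Q2W is the PD signal that bears on it. The first 24 weeks of reduction belong to the parent study. This stands as a reason to keep the summary, but a maintenance summary does not stand in for the PD effect named in the objective.

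A second defence is that percent change is not the only PD output. Actual values and the minimum post-baseline value are planned, baseline IgG is reported, and exposure-response work using IgG may follow under a separate plan. The former-placebo column starts undrugged and can be set against 60% to 70% for those on QW. All of this stands. Actual values also allow a rough group comparison with the former-placebo group's untreated baseline. They do not give within-person percent reduction, which is the named endpoint.

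Three stronger readings are tempting, and the documents do not support them:
- A reader might infer that the whole reported PD effect will be near zero or reversed. The former-placebo column and the all-QW pooled figure above contradict that, and any reversal depends on a Q2W reduction that is nowhere stated.
- A reader might infer that the study then has no valid PD measure. The actual values and the former-placebo column rule that out.
- SAP 9 lists "Anti-La/SS-B positive" as a baseline characteristic, and SAP 6.7 says: "For participants with a baseline PD value below/above the quantification limit, the PD parameter will be excluded from the statistical analyses involving change". A reader might infer that seronegative participants distort the autoantibody results, or that participants already driven below the limit are lost. The documents give neither assay limits nor numbers of seronegatives, so neither effect can be shown or sized.

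Lastly, SAP 6.2 allows exceptions and refers to Appendix 1, which was not in the text available, and some SAP sections are redacted. An output from the parent baseline could be specified there. No visible section plans one.

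**Conclusion.** The point holds for two of the three columns. For former-efgartigimod participants, the SAP 14 change, percent change and maximum drop from baseline measure maintenance from a suppressed level. The pooled column mixes that with a true reduction in the former-placebo group.

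If 60% to 70% applies to total IgG in this population, the former-efgartigimod column reads about 0% on unchanged QW, and the pooled column about −20% to −23% with everyone on QW. Both would read −60% to −70% from an untreated baseline. Any rise on Q2W is conditional on an assumed loss of suppression. The result also rests on equal rollover by arm and on carrying the reduction over from other populations.

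The study is descriptive and tests no hypothesis, so no error rate, power or sample size is affected. What is at risk is the meaning of a named secondary endpoint for the expected majority of participants, and the correction is cheap.

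**What to change.** In SAP 14:
- Add change, percent change and maximum drop from the ARGX-113-2106 pre-dose baseline for total IgG, anti-Ro/SS-A and anti-La/SS-B, at least for former-efgartigimod participants.
- For these summaries, apply the SAP 6.7 quantification-limit rule to the pre-dose value.
- Keep change from OLE baseline by parent arm, labelled as maintenance for former-efgartigimod participants.
- State that the pooled percent change from OLE baseline is not to be read as the PD effect.

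Before editing, confirm that SAP Appendix 1 does not already specify this output.

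The cost is one extra merge of parent-study PD data and one extra set of summaries. The SAP already uses parent-study values and allocation (SAP 6.2, 7.2 and 9.1). No new samples or visits are needed.
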